7.8 Accepted Therapies

During the experimental treatment period, any medications considered essential for the treatment of any concomitant diseases may be administered.

Any changes in dosage and/or new concomitant therapies will only be introduced if strictly necessary, and must be reported on the Patient's Medical Record and the study CRF.

7.9 Non-accepted therapies

The administration of medications that may interfere with the assessment of oral Citicoline supplements or which could alter the evaluation of efficacy parameters, and in particular medications with potential effects on retinal or macular function or nerve conduction along the optic pathways, such as:

- cerebral vasoactives
- neurotrophics
- lutein, zeaxanthin, retinals
- docosahexaenoic acid
- ubiquinone and/or its derivatives, may not be administered.

Any previous treatment with Ubiquinone, L-Carnitine, Citicoline and/or its derivatives in other formulations and/or dosages must have been discontinued at least 6 months prior to inclusion in the study.

7.10 Compliance with treatment

The importance of taking the Citicoline supplement on a regular basis should be emphasised by the Investigator to the patient, who, pursuant to signing the informed consent, must also be instructed to return unused and/or excess samples (vials) at follow-up visits to the visit at which they were consigned, in line with the study timing.

The Investigator can thus compile, both during the control visits and at the end of the study, the section of the CRF in which compliance with the prescription is recorded, calculate compliance with the treatment and provide for the storage of the returned material in a place accessible to authorised persons only.

Compliance assessment will be carried out by counting the dosage units returned by the patient as unused (vials not taken) and calculating the ratio between the number of vials taken and the

number of vials that should have been taken according to the dosage schedule envisaged by the protocol.

Depending on compliance, all patients who have taken at least 80% of the planned dose regimen will be considered compliant with treatment.

7.11 Suspension/interruption of treatment

The food supplement may be discontinued spontaneously by the patient at any time he/she deems appropriate or upon decision of the Investigator (the patient will be considered “drop-out”) should his/her clinical conditions require. Any discontinuation must be fully documented in the CRF by the Investigator.

Treatment may be discontinued prematurely for the following reasons:

- refusal of the patient to continue treatment;
- the occurrence of an Incident that may interfere with the patient's assessment or cause the continuation of the study to be considered inappropriate;
- logistical variations that make it impossible for the patient to participate in the study.

It will be the Investigator's responsibility to follow-up patients after discontinuation for an appropriate period of time (30 days) to assess their clinical conditions and/or verify the occurrence of Incidents even after the end of the trial therapy.

It is also recommended that these patients carry out the check-ups envisaged for the end of the study, since they will equally be considered for the intention-to-treat analysis.

For each of the patients who drops out of the trial, all available documentation will however be collected, where clinically possible, until they leave the study.

8. ASSESSMENT OF SAFETY AND TOLERABILITY

8.1 Safety and Tolerability

Neukron Ofta® mese, used in the present study, is a Cisticoline-based food supplement.

The tolerability of Cisticoline by the human body is well known since it is an endogenous substance, and has so far been administered intravenously, intramuscularly, orally and topically (Secades 2001). No adverse events attributable to the administration of such Cisticoline-based supplement have been reported to date.

The only warnings are not to take Neukron Ofta® mese during pregnancy and lactation, as the possible effects on the fetus and/or newborn are not fully known.

For this reason, pregnant or breast-feeding women cannot participate in the study; at the same time, women of childbearing age must agree to the use of adequate contraception methods throughout the duration of treatment with Cisticoline envisaged by the study; for the safety of patients it should be emphasised that scientifically accepted birth control methods do not provide absolute protection: some women have become pregnant even with the regular use of these types of methods.

However, despite our experience and that of others (Parisi et al. 1999, Porciatti et al. 1998, Campos et al. 1995, Campos 1997, Virno et al. 2000, Rejdak et al. 2003 leading us to assume that no patient should suffer adverse events, throughout the duration of the study, particular attention will be paid to patients' descriptions of their general conditions (e.g. increase/decrease in systemic blood pressure, gastric pyrosis, skin rashes, etc...)

The safety and tolerability of the food supplement will be evaluated at the end of the study, analysing all the information collected.

All this information will be recorded on the appropriate CRF, at the times and in the manner described in the dedicated sections of this protocol.

8.2 Incidents or Near-Incidents

Clinical tolerability to treatment will be assessed by recording the occurrence of incidents or near-Incidents reported by the Patient or observed by the Investigator. This registration will be made from the moment the patient signs the informed consent.

All Incidents occurring during the clinical trial must be reported on the CRF.

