8.2.1 Definitions

a) Incident

Also taking into account the European guideline on vigilance "incident" means the condition in which any malfunction or deterioration in the characteristics and/or performance, as well as any inadequacy in the labelling or the instructions for use of a food supplement has led, directly or indirectly, to the death of a patient or user or to a serious deterioration in their state of health.

Serious deterioration of state of health means: a life-threatening illness or injury; an impairment of a bodily function or injury to a body structure; a condition that requires medical or surgical intervention to prevent an impairment of a bodily function or injury to a body structure; a condition that causes hospitalization or the extension of hospitalization.

b) Near-Incident

A near-incident means: (a) the condition in which any malfunction or deterioration in the characteristics or performance, as well as any inadequacy in the labelling or instructions for use of a food supplement, could have caused, directly or indirectly, if the food supplement had been used, a serious deterioration of the state of health or death of the patient or user; (b) the condition in which any malfunction or deterioration in the characteristics or performance, as well as any inadequacy in the labelling or instructions for use of a food supplement, could have caused, during use or as a result of use, a serious deterioration in the state of health or death of the patient or a user, had the health care professional not intervened.

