8.2.2 Incident or near-incident reporting

Investigators involved in the clinical trial are required to complete the standard section for gathering information on Incidents or near-Incidents in the CRF of the study.

a) Methods of communicating the Incident or Near-Incident

Upon the occurrence of an incident or near-incident, the Investigator must complete the CRF page for reporting all Incidents and near-incidents and the appropriate form (Incident or near-incident report by health care professionals to the Ministry of Health) relative to the reporting of Incidents caused by taking food supplements.

This Form, accompanied by a duly compiled submission form, must be sent by [contact]) within 24 hours of knowledge of the incident to the Hospital Department of Visual Neurophysiology and Neurophthalmology, Bietti-IRCCS

Foundation, which will directly inform the persons responsible for monitoring medical devices of the Ministry of Health.

b) Further Investigations

The Investigator and the other persons responsible for Patient health must conduct any further investigation of Incidents or Near-Incidents, based on their clinical judgement of the likely causal factors.

c) Regulatory aspects

The Bietti-IRCCS Foundation is responsible for reporting to the competent Health Authorities any information relating to the safety of its medications. It is therefore essential for the Investigator to promptly report any Incident or Near-Incident, in order to allow it to comply with such requirements.

These responsibilities are accepted by the Investigator as per the conditions set out in this protocol.

d) Instructions for Compiling the Forms Provided

For the compilation of the CRF page as well as the incident or near-incident report by health care professionals to the Ministry of Health, the Investigator should refer to the instructions provided to him/her together with such forms.

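### The only defined tolerability measure requires a product or labelling fault, so ordinary reactions and serious events on a sound product fall outside it

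*Combined protocol and SAP*

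**What the plan says.** Section 8.2 sets the measure: "Clinical tolerability to treatment will be assessed by recording the occurrence of incidents or near-Incidents reported by the Patient or observed by the Investigator". Recording starts at consent, and every Incident goes on the CRF.

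Section 8.2.1 defines the two terms. An incident needs a "malfunction or deterioration in the characteristics and/or performance, as well as any inadequacy in the labelling or the instructions for use" of a food supplement that "has led, directly or indirectly, to the death of a patient or user or to a serious deterioration in their state of health". A near-incident needs the same kind of fault, but the harm need only be potential. Its first limb covers a fault that "could have caused, directly or indirectly, if the food supplement had been used, a serious deterioration of the state of health" or death; its second covers harm averted because a professional stepped in.

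Section 8.1 is broader. It asks for attention to patients' accounts of their general condition and gives blood-pressure changes, gastric pyrosis and skin rashes as examples. It says safety will be judged at the end of the study on everything collected. For recording, it says that this information goes on the CRF "at the times and in the manner described in the dedicated sections of this protocol".

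Section 8.2.2 requires the incident or near-incident form to be sent "within 24 hours of knowledge of the incident". The schedule in section 5.2 has a row for Incidents and no row for adverse events. No adverse event or serious adverse event is defined anywhere, and there is no grading of severity or causality. Section 9.2 describes no safety analysis.

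**The concern.** The definitions are those of product vigilance. They answer the question of whether a faulty or badly labelled product harmed someone, or could have. A tolerability assessment asks something else: what untoward events occur in people who take the product as intended, and are they more frequent than in people who do not take it?

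If the defined measure is applied as written, the reactions most likely to matter for a daily oral supplement do not count. A serious medical event with no product fault does not set off the prompt report. The untreated group supplies no background rate against which complaints in the treated group could be judged. A final report stating few or no incidents would be accurate on its own terms, yet could be taken as evidence of good tolerability.

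**Working it through.** The plan states no figure for safety, and the point depends on no sample size or event rate. The check is therefore a reading of the definitions against the other sections.

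**Step 1: separate the two elements.** Both terms need (i) a fault in the product, label or instructions, and (ii) death or serious deterioration, actual for an incident and potential for a near-incident. Element (ii) is fairly wide, because the list of serious deteriorations includes impairment of a bodily function without requiring that it be permanent. Element (i) is what excludes most clinical events.

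**Step 2: apply the definitions to typical events.**

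| Event | Product or label fault | Status under 8.2.1 | 24-hour report | Other route in the protocol |
|---|---|---|---|---|
| Rash or pyrosis, sound vial, no medication | No | Neither | No | General promise in 8.1 |
| The same, medication needed | No | Neither | No | The medication is entered under systemic therapies (7.7) |
| Hospital admission, sound vial | No | Neither | No | Perhaps the concomitant-disease row; discontinuation record if treatment stops (7.11) |
| Faulty vial, serious harm possible but absent | Yes | Near-incident | Yes | None needed |
| Faulty vial leading to hospital admission | Yes | Incident | Yes | None needed |
| Overdose of sound product, no incident | No | Neither | No | Report to the coordinating department, no time limit given (8.2.3) |
| Hospital admission, control patient | No study product taken | Neither, by inference | No | Perhaps the concomitant-disease row |

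**Step 3: follow the reference in 8.1.** Section 8.1 names the complaints and leaves the manner of recording to dedicated sections. The only section dedicated to recording events is 8.2. The reference thus leads back to a definition that leaves out the examples in 8.1. The two sections do not agree.

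**Step 4: test the partial routes.**
- Concomitant diseases and concomitant treatments are collected at baseline, 6 and 9 months in every patient (5.2), but nothing designates them as safety data.
- Section 7.7 captures a medication rather than the event. It misses untreated symptoms and is worded around starting the supplement, so it does not fit controls.
- Section 7.11 documents discontinuations and follows those patients for 30 days.
- Section 8.2.3 goes beyond incidents for overdose only.

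None of these is defined as a safety outcome or compared between arms.

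**Step 5: check consistency of the term.** Section 8.2.2 refers to a form for Incidents caused by taking food supplements, and section 8.2.3 to overdoses that lead to Incidents. Neither use implies a fault in the product. Two investigators could therefore classify the same reaction differently.

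**Step 6: controls.** Section 5.1 gives them no treatment. Sections 5.2 and 8.2 apply the recording to all consenting patients, so collection in both arms seems intended. A definition built on a supplement fault leaves little that a control could contribute.

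**The case against.** The strongest reply is that the protocol as a whole is wider than 8.2.1. Section 8.1 names ordinary complaints, promises CRF recording and evaluates all the information. Several CRF entries would pick up traces of an event. The looser use of Incident in 8.2.2 and 8.2.3 suggests that investigators may record reactions anyway. The CRF and its completion instructions are not among the documents, so actual practice cannot be checked. Safety is also not a listed objective in sections 2.1, 2.2 or 5.5.

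Much of this stands, and it rules out several stronger readings that a reader might infer:
- *That ordinary reactions go unrecorded altogether.* They are outside the defined measure, but 8.1 and the partial routes mean they are not outside the whole plan.
- *That every countable event needs actual serious harm.* Near-incidents need only the potential for it.
- *That the protocol excludes control-arm events by rule.* It does not. The exclusion is inferred from the definition and from the lack of study product in that arm, and the definition speaks of a food supplement in general.
- *That the count must be near zero whatever the true rate.* This follows only if every investigator applies 8.2.1 strictly.
- *That the gap can be sized by the upper confidence limit for zero events.* That limit reflects the number of patients and would be the same after the correction. The documents supply no reaction rate from which to estimate missed events.

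The reply does not reconcile 8.1 with 8.2. A promise to analyse everything collected has little force when the only defined event excludes the examples given. One further objection bears on the remedy: assessors are masked and patients undertake not to reveal their group to them (section 6), so careless questioning about reactions could unmask them.

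**Conclusion.** The concern holds in a limited form. The only defined tolerability measure depends on a product, labelling or instruction fault. Ordinary reactions to a sound product and serious medical events without a fault are outside it and outside the 24-hour report; by inference, so are control-arm events. Sections 8.1 and 8.2/8.2.1 conflict, and 8.1 has no definition, form or by-arm analysis of its own.

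The consequence is qualitative: a low incident count cannot support a statement about tolerability, and serious events without a product fault have no defined prompt route. No numerical size is claimed. The efficacy analysis is unaffected. The conclusion rests on reading 8.2.1 as written and on the CRF instructions, which are not available here, adding no broader definition. The definitional finding is firm; how much would be missed in practice is uncertain.

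**What to change.** Reconcile 8.1 with 8.2 and 8.2.1:

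- Add standard definitions of adverse event and serious adverse event: any untoward medical occurrence from consent to the 9-month visit, in both arms, whatever the cause or the condition of the product.
- Make these the tolerability measure and tabulate them by arm. State this in section 9.2.
- Extend the existing prompt-report route in 8.2.2 to serious adverse events.
- Keep product incidents and near-incidents as a subset, and use the term consistently in 8.2.2 and 8.2.3.
- Rename the Incidents row of the schedule to match.
- Assign collection to the recruiting doctor, who already knows the allocation, and not to the masked assessors.

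The cost is protocol wording, one CRF page and modest extra recording and reporting at visits already planned. Because patients and the recruiting doctor know the allocation, ascertainment will not be masked, so the same questions should be put to both arms and the by-arm table read as descriptive.

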8.2.1 Definitions

a) Incident

Also taking into account the European guideline on vigilance "incident" means the condition in which any malfunction or deterioration in the characteristics and/or performance, as well as any inadequacy in the labelling or the instructions for use of a food supplement has led, directly or indirectly, to the death of a patient or user or to a serious deterioration in their state of health.

Serious deterioration of state of health means: a life-threatening illness or injury; an impairment of a bodily function or injury to a body structure; a condition that requires medical or surgical intervention to prevent an impairment of a bodily function or injury to a body structure; a condition that causes hospitalization or the extension of hospitalization.

b) Near-Incident

A near-incident means: (a) the condition in which any malfunction or deterioration in the characteristics or performance, as well as any inadequacy in the labelling or instructions for use of a food supplement, could have caused, directly or indirectly, if the food supplement had been used, a serious deterioration of the state of health or death of the patient or user; (b) the condition in which any malfunction or deterioration in the characteristics or performance, as well as any inadequacy in the labelling or instructions for use of a food supplement, could have caused, during use or as a result of use, a serious deterioration in the state of health or death of the patient or a user, had the health care professional not intervened.

8.2.2 Incident or near-incident reporting

Investigators involved in the clinical trial are required to complete the standard section for gathering information on Incidents or near-Incidents in the CRF of the study.

a) Methods of communicating the Incident or Near-Incident

Upon the occurrence of an incident or near-incident, the Investigator must complete the CRF page for reporting all Incidents and near-incidents and the appropriate form (Incident or near-incident report by health care professionals to the Ministry of Health) relative to the reporting of Incidents caused by taking food supplements.

This Form, accompanied by a duly compiled submission form, must be sent by [contact]) within 24 hours of knowledge of the incident to the Hospital Department of Visual Neurophysiology and Neurophthalmology, Bietti-IRCCS

Foundation, which will directly inform the persons responsible for monitoring medical devices of the Ministry of Health.

b) Further Investigations

The Investigator and the other persons responsible for Patient health must conduct any further investigation of Incidents or Near-Incidents, based on their clinical judgement of the likely causal factors.

c) Regulatory aspects

The Bietti-IRCCS Foundation is responsible for reporting to the competent Health Authorities any information relating to the safety of its medications. It is therefore essential for the Investigator to promptly report any Incident or Near-Incident, in order to allow it to comply with such requirements.

These responsibilities are accepted by the Investigator as per the conditions set out in this protocol.

d) Instructions for Compiling the Forms Provided

For the compilation of the CRF page as well as the incident or near-incident report by health care professionals to the Ministry of Health, the Investigator should refer to the instructions provided to him/her together with such forms.

8.2.3 Overdose

Cases of overdose (accidental or intentional) leading to Incidents or near- incidents should be managed according to emergency procedures. This includes reports of food supplement intake for suicidal purposes with consequent overdose of such food supplement.

Reports of overdose not associated with incidents should also be reported to the
Hospital Department of Visual Neurophysiology and Neuroophthalmology, Bietti-IRCCS Foundation,

(although not requiring notification to Regulatory Authorities), in order to obtain information on symptoms, corrective treatment and the outcome of such an overdose.

9. STATISTICAL ANALYSIS

9.1 Sample size

The sample size is estimated based on the primary objective: 'assessment of stabilisation and/or improvement of visual acuity' (see section 2.1.).

This calculation is based on known preliminary data (Parisi et al, 2008), in which visual acuity was assessed through Early Treatment Diabetic Retinopathy Study (ETDRS) cards and the acquired value has been expressed in LogMAR (logarithm of the minimum angle of resolution).

Based on these known preliminary data (Parisi et al, 2008), and considering a power value = 90% ($\alpha = 5\%$) it is deemed reasonable to include in the study $N = 5$ observations (eyes tested) per group.

The sample size has been calculated based on the difference in visual acuity measured in patients with NAION after 60 days of treatment with Citicoline in oral suspension compared to the baseline of 0.35 LogMAR (baseline visual acuity: mean 0.621 LogMAR, a standard deviation: 0.122 LogMAR; visual acuity at 60 days: mean 0.271 LogMAR, a standard deviation: 0.107 LogMAR).

However, based on the secondary objective-point 2 (see section 2.2) 'to determine in patients with NAION the potential for neuroenhancement related to the administration of Citicoline oral solution. This will be achieved through functional condition assessments (PERG/VEP) measured after treatment with Citicoline compared to the condition at the time of recruitment", it is considered appropriate to assess the sample size taking into account the known preliminary data (Parisi et al, 2008) in which they were analysed:

- a) changes in the functionality of retinal ganglion cells by measuring the Amplitude P50-N95 (measured in microvolts) obtained by recording the ERG from Pattern (PERG).
- b) changes in optic nerve function by measuring Implicit Time P100 (measured in milliseconds, ms) obtained by recording Visual Evoked Potential (VEP).

Based on known preliminary data (Parisi et al, 2008), considering the P50-N95 amplitude of the PERG and a power value = 90% ($\alpha = 5\%$) it is reasonable to include in study $N = 12$ observations (eyes tested) per group. The sample number has been calculated based on the difference in the P50-N95 amplitude of the PERG measured after 60 days of treatment with Citicoline for oral suspension compared to the baseline of 0.38 microvolts (Baseline P50-N95: mean 0.92 microvolts, a standard deviation: 0.29 microvolts; P50-N95 at 60 days: mean 1.30 microvolts, a standard deviation: 0.25 microvolts).

Based on known preliminary data (Parisi et al, 2008), considering the implicit time P100 of the VEP and a power value = 90% ($\alpha = 5\%$) it is deemed reasonable to include in the study $N = 11$ observations (eyes tested) per group. The sample number has been calculated based on the difference in the implicit time P100 of the VEP measured after 60 days of treatment with Cisticoline for oral suspension compared to the baseline of 15 ms (Baseline P100: mean 141 ms, a standard deviation; P100 at 60 days: mean 126 ms, a standard deviation: 9.8 ms).

To summarise, the size from the sample estimated on the basis of the primary objective (visual acuity) is $N= 5$; the size from the sample estimated on the basis of secondary objectives (PERG and VEP) is $N=12$ and $N=11$, respectively.

Considering the larger sample size ($N=12$, PERG), and assuming the presence of outliers and the potential voluntary withdrawal from the study by patients, the sample is increased by 30%, so it is considered appropriate to reach $N=16$ observations (eyes tested) per group (NAION Treated with Cisticoline and NAION not treated).

In this calculation of the sample, it is not possible to estimate a priori the sample number relative to the secondary objective – point 3 (see Point 2.2), as data in the literature are not currently available regarding possible changes in the structure of nerve fibres and the optic nerve (assessed by OCT) following treatment with Cisticoline.

The calculation procedure was carried out using the Minitab v.12.7 and Gpower 3.1 programmes, assuming that the averages and standard deviations of all the parameters considered come from two independent samples: Patients with NAION in baseline condition and patients with NAION after 60 days of treatment with Cisticoline in oral suspension (Parisi et al, 2008).

